## 9.4 Pharmacodynamic Assessment

### 9.4.1 Pharmacodynamic Analysis

Noncompartmental methods applied with a validated software program Phoenix WinNonlin (Pharsight Corporation, Version 6.4 or higher) to the plasma concentrations of CGRP and will be used to determine the following PD parameters, when possible:

Parameter	Units	Definition
AUC(0-t last ), CGRP	day×ng/mL	area under the concentration versus time curve of CGRP from time zero to time t, where t is the last time point with a measurable concentration
C max , CGRP	ng/mL	maximum observed concentration of CGRP
t max , CGRP	day	time of maximum observed concentration of CGRP

The same general rules outlined in section 9.3.1.1 will be used for derivation of the PD parameters, where appropriate. The PD parameters will be listed for individual subjects, and summary statistics will be computed by treatment (PFS, AI) and injection site location (arm, abdomen, thigh, buttocks).

#### **9.4.2 Pharmacodynamic Statistical Methodology**

Log-transformed CGRP  $C_{max}$  and  $AUC(0-t_{last})$  estimates will be evaluated by an ANOVA with fixed effects for injection device (PFS [reference] or AI [test]), investigative site, and injection site. The least squares means for PFS and AI and the 90% CI for the difference in means will be estimated from the ANOVA model and back transformed from the log scale to provide estimates of the geometric means and 90% CIs for the ratio of the geometric means. Similar SAS code to that for the PK analysis will be used.

The CGRP  $t_{max}$  between injection devices (PFS [reference] or AI [test]) will be analyzed using a Wilcoxon rank-sum test. An estimate of the median difference and 90% CI will be calculated.

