Log-transformed C_{max} , CGRP and $AUC(0-t_{last}, CGRP)$ estimates will be evaluated by an ANOVA with fixed effects for injection device (PFS [reference] or autoinjector [test]), investigative site, and injection site. The least squares means for PFS and autoinjector and the 90% CI for the difference in means will be estimated from the ANOVA model and back transformed from the log scale to provide estimates of the geometric means and 90% CIs for the ratio of the geometric means.

2. Schedule of Activities

Study Schedule Protocol I5Q-MC-CGAQ

Weeks Postdose			0					1			2	3	4	6	8	10	12	16	20
Day	SC ^a	- 1	1	2	3	5	6	8	10	12	15	22	29	43	57	71	85	113	141 ^b
Visit Window (days)											±1	±2	±2	±3	±3	±3	±3	±3	±3
CRU admission ^c		X																	
CRU discharge ^c				X															
Outpatient visit ^d	X				X	X	X	X	X	X	X	X	X	X	X	X	X	X	X
Randomization			X																
Study drug injection			X ^e																
Informed consent	X																		
Eligibility assessment	X																		
Medical history	X																		
Recording of AEs	X	X	X	X	X	X	X	X	X	X	X	X	X	X	X	X	X	X	X
Concomitant medication	X	X	X	X	X	X	X	X	X	X	X	X	X	X	X	X	X	X	X
Physical exam ^f	X	X	Predose	X				X			X		X	X	X		X	X	X
Body temperature	X	X																	
Height, weight ^g	X		Predose																X
Vital signs (hours) ^h	X	X	Predose, 8	24		X		X			X		X	X	X		X	X	X
Single 12-lead ECG	X	X		24														X	X
Clinical laboratory tests	X	X									X				X			X	X
Serology: HIV, HBV, HCV	X																		
Urine drug screen, ethanol test ⁱ & pregnancy test ^j	X	X																X	X
LY2951742 PK blood sampling (hours) ^k			8	24	48	96	120	168	216	264	336	504	672	1008	1344	1680	2016	2688	3360
Plasma CGRP sampling for PD (hours) ^l			Predose	24	48	96	120	168	216	264	336	504	672	1008	1344	1680	2016	2688	3360
PGx blood sampling			Predose																
Immunogenicity blood sampling (hours)			Predose								336		672		1344		2016		3360

Abbreviations: AE = adverse event; CRU = clinical research unit; ECG = electrocardiogram; HBV = hepatitis B virus; HCV = hepatitis C virus; HIV = human immunodeficiency virus; PD = pharmacodynamics; PK = pharmacokinetics; PGx = pharmacogenetics; SC = screening.

- a Screening visit to be conducted within 45 days prior to dosing.
- b End-of-study visit. Also, procedures for early termination.
- c Subjects will be admitted to the CRU on Day -1, and may be discharged on Day 2 after the procedures scheduled at 24 hours after dosing have been completed.

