- d Unless otherwise specified, safety monitoring procedures throughout the study should be performed at approximately the same time of day (± 2 hours) as dosing was performed on Day 1 (except for procedures scheduled at screening and Day -1).
- e Each subject will receive a single dose of 240 mg LY2951742 in the morning, administered as 2×1 -mL (120 mg/mL) subcutaneous injections of solution formulation in either a manual prefilled syringe or an autoinjector device. Injection-site reactions after injection will be assessed as part of AE collection.
- f Complete physical examination to be performed at screening and at the final visit for each subject; directed physical examination only at other visits and as clinically indicated.
- g Height to be measured at screening only.
- h Vital signs include sitting blood pressure and pulse rate.
- i Additional urine drug screen and ethanol tests may be performed at the investigator's discretion.
- j Required for females of child-bearing potential only; however, pregnancy tests carried out in females of non-childbearing potential pending receipt of follicle-stimulating hormone results will not be considered a protocol deviation. Serum pregnancy test will be done on screening, and may be repeated using urine or serum test prior to admission to the clinical research unit and as clinically indicated.
- k When possible, PK samples on follow-up outpatient visit days should be collected at a time of day close to when dosing occurred on Day 1 (± 2 hours). PK sampling times are given as targets to be achieved within reasonable limits. The actual time of PK sampling should be recorded.
- l Baseline plasma CGRP sample will be taken on Day 1 prior to study drug injection.

3. Introduction

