3.2. Background

LY2951742 is a humanized monoclonal antibody that potently and selectively binds to calcitonin gene-related peptide (CGRP), a peptide that is widely expressed in the central and peripheral nervous system and acts as a local facilitator of inflammatory processes. Therefore, neutralizing CGRP is anticipated to modulate neurogenic inflammation and is considered a therapeutic approach for the treatment of migraine and neuropathic pain. As such, Lilly is currently evaluating LY2951742 for migraine prevention and cluster headache prevention.

Clinical Experience with LY2951742

LY2951742 was administered via the subcutaneous route using a lyophilized formulation in the following completed clinical trials:

In a Phase 1, single ascending-dose and multiple-dose study (I5Q-MC-CGAA), LY2951742 was administered to healthy subjects as single doses from 1 to 600 mg, and 150 mg every 2 weeks (Q2W) for a total of 4 administrations. LY2951742 appeared to be well tolerated and did not result in any serious adverse events (SAEs) or discontinuations due to treatment-emergent adverse events (TEAEs). All TEAEs were mild in severity and the incidence of TEAEs did not increase with higher dose. For the LY2951742-treated subjects, 11 (26%) in the single-dose cohorts, and 4 (57%) in the multiple-dose cohort developed drug-induced anti-drug antibodies (ADA) and there was no apparent effect of these findings on the safety, tolerability, PK, or PD (plasma CGRP concentration) of LY2951742.

In a Phase 1 study (I5Q-MC-CGAE), LY2951742 was administered to Japanese and Caucasian subjects to evaluate the safety, tolerability, PK, and PD of LY2951742 after a single dose of 5 to 300 mg and multiple doses of 300 mg every 4 weeks (Q4W). The data indicated that there are no clinically significant safety findings in these populations, and the PK and PD profiles were comparable.

In a Phase 2a study (I5Q-AR-ART1 [ART-01]), LY2951742 given at a dose of 150 mg Q2W for 12 weeks was effective as compared with placebo in reducing the number of migraine headache days, headache hours, and the number of migraine attacks in patients with episodic migraines. LY2951742 was well tolerated in migraineurs, with no notable safety findings. No findings of clinical importance on the basis of efficacy, tolerability, PK, and safety were noted with regard to the formation of treatment-emergent ADA.

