In Study CGAA, PD assessments were performed in healthy subjects following single and multiple doses by evaluating the inhibition in capsaicin-induced dermal blood flow (CIDBF). Dermal blood flow was determined using Laser Doppler Imaging. In general, the 75, 200, and 600 mg doses appeared to elicit a maximum inhibition of CIDBF and this effect was sustained when measured 42 days after a single dose; following repeated doses, the effect on CIDBF was sustained for at least 144 days after the last of four 150-mg subcutaneous injections administered Q2W.

In Studies CGAA and CGAB, total CGRP plasma concentrations were measured following multiple doses of LY2951742. Concentrations of CGRP increased in an LY2951742 dose- and concentration-dependent manner, suggesting binding of LY2951742 to CGRP.

Characteristics of the PFS and Autoinjector

Lilly is evaluating 2 delivery methods for subcutaneous injections of LY2951742, including a glass PFS with a staked (permanently affixed) needle for manual injection, and a glass PFS with a staked needle pre-assembled in an investigational autoinjector. The PFS, including the glass barrel, plunger, and needle, will be identical for the 2 devices and will contain 120 mg LY2951742.

A volume of 1.0 mL containing 120 mg LY2951742 will be filled into a 1.0 mL glass syringe with a 12.7 mm, 27-gauge, thin-wall, stainless steel staked needle. The syringe will be closed at the product contact surface with an elastomeric plunger. The PFS needle will be protected and closed by a rigid needle shield consisting of an elastomeric core with a rigid polypropylene shell. The syringe, needle, and plunger (non-product contact surface) are lubricated. The PFS will be assembled inside the autoinjector, so there will not be a difference in the product contact surfaces.

More information about the known and expected benefits, risks, and reasonably anticipated AEs may be found in the device Investigator's Brochure (IB). Information on AEs expected to be related to the study device may be found in Section 7 (Development Core Safety Information) of the device IB.

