10.3.3.2. Pharmacodynamic Statistical Inference

Log-transformed $C_{\max, \text{CGRP}}$ and $AUC(0-t_{\text{last, CGRP}})$ estimates will be evaluated by an ANOVA with fixed effects for injection device (PFS [reference] or autoinjector [test]), investigative site, and injection site. The least squares means for PFS and autoinjector and the 90% CI for the difference in means will be estimated from the ANOVA model and back transformed from the log scale to provide estimates of the geometric means and 90% CIs for the ratio of the geometric means.

The $t_{\max, \text{CGRP}}$ between injection devices (PFS [reference] or autoinjector [test]) will be analyzed using a Wilcoxon rank-sum test. An estimate of the median difference and 90% CI will be calculated.

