#### 4.2 Secondary Objectives

- To assess plasma calcitonin gene-related peptide (CGRP) concentrations after SC administration of 240 mg LY2951742 solution as a PFS or AI.
- To assess the safety and tolerability of LY2951742 in healthy subjects after SC administration of 240 mg LY2951742 solution as a manual PFS or AI.

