## 7. SAMPLE SIZE JUSTIFICATION

Up to 160 subjects will be enrolled (80 in each arm). The number of subjects was determined on the basis of Study I5Q-MC-CGAO Part B interim data, a Phase 1 single-dose study evaluating 300 mg LY2951742 solution administered as a PFS. The percent coefficient of variation for LY2951742 maximum observed drug concentration ( $C_{max}$ ) and area under the concentration versus time curve from zero to infinity ( $AUC_{0-\infty}$ ) was approximately 35%. One-hundred sixty (160) subjects (80 per arm) will provide approximately 90% power to demonstrate that the 90% confidence interval (CI) of the ratio of geometric means between test and reference devices for the PK parameter falls within 0.8 to 1.25, assuming the true ratio is 0.95 and 12.5% of subjects will not contribute to the endpoint. Randomized and dosed subjects with insufficient collection of PK samples may be replaced at the discretion of the sponsor.

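### The PD model for CGRP omits the predose CGRP value that every subject is scheduled to give; adding it is a cheap, optional gain in precision

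*SAP*

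**What the plan says.** SAP 9.4.2 says that the two log-transformed CGRP parameters "will be evaluated by an ANOVA with fixed effects for injection device (PFS [reference] or AI [test]), investigative site, and injection site", with code similar to the PK code. That code (SAP 9.3.2) has three class effects and no covariate. Protocol 10.3.3.2 specifies the same "ANOVA with fixed effects for injection device (PFS [reference] or autoinjector [test]), investigative site, and injection site", so the documents agree.

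The parameters are observed values with no baseline correction (SAP 9.4.1). The predose value can enter AUC(0-tlast) as its time-zero point, through the general rules of SAP 9.3.1.1, but it has no place in the model.

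The protocol describes CGRP as "a peptide that is widely expressed in the central and peripheral nervous system", so subjects have a level before dosing. Footnote l to the Schedule of Activities says: "Baseline plasma CGRP sample will be taken on Day 1 prior to study drug injection".

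The role of this analysis is secondary. SAP 4.2 words the objective as "To assess plasma calcitonin gene-related peptide (CGRP) concentrations after SC administration of 240 mg LY2951742 solution as a PFS or AI". The only acceptance range in either document is in the sample-size text, where it is the interval "for the PK parameter falls within 0.8 to 1.25".

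**The concern.** The comparison is between subjects in two parallel arms. Any variation in post-dose CGRP that baseline predicts, beyond device, investigative site and injection site, stays in the residual error and widens the 90% interval for the device ratio. The measurement that could remove it is already scheduled. If baseline is a strong predictor, the PD interval is wider than it need be, at no saving.

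What is at stake is the width of the interval for a secondary endpoint. The PK model has no such gap, because no predose drug sample is scheduled.

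**Working it through.** **1. The plan's own figure.** The stated power of about 90% is for PK. With CV 35%, log SD = sqrt(ln(1 + 0.35^2)) = 0.340. Evaluable subjects = 160 x 0.875 = 140, or 70 per arm, so SE = 0.340 x sqrt(2/70) = 0.0575. At a true ratio of 0.95 and 5% per side, power by normal approximation = Phi[ln(0.95/0.80)/0.0575 - 1.645] + Phi[ln(1.25/0.95)/0.0575 - 1.645] - 1 = 0.910. The stated figure is reproduced, and it does not involve the PD model. No power is stated for PD.

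**2. Inputs for the PD check.**
- N = 140 evaluable for PD. This is an assumption: the 12.5% non-contribution rate is given only in the PK power sentence.
- Number of sites S: not given; 2 to 10 assumed, 4 used below.
- r: the partial correlation of log baseline with log post-dose CGRP, given the three model terms. Not given; 0 to 0.7 assumed.
- CGRP CV: not given; 25%, 35% and 50% assumed.

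**3. Change in half-width.** Residual degrees of freedom of the planned ANOVA: f = N - 1 - 1 - (S - 1) - 2 = 140 - 1 - 1 - 3 - 2 = 133. With k added terms, the expected half-width relative to the planned model is sqrt[(1 - r^2)(1 + k/(f - k - 1))] x t(0.95, f - k)/t(0.95, f). Here k = 1 is log baseline alone and k = 2 adds a below-limit indicator.

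| r | k = 1 | k = 2 | equivalent N, k = 1 (140/ratio^2) |
|---|---|---|---|
| 0 | 1.0039 | 1.0078 | 139 |
| 0.2 | 0.9836 | 0.9874 | 145 |
| 0.3 | 0.9576 | 0.9614 | 153 |
| 0.5 | 0.8694 | 0.8728 | 185 |
| 0.7 | 0.7169 | 0.7197 | 272 |

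Moving S between 2 and 10 changes these ratios by at most 0.0005. The covariate breaks even at r of about 0.09 (one term) or 0.12 (two terms).

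**4. On the ratio scale.** The limits are the estimated ratio multiplied and divided by exp[1.656 x log SD x sqrt(2/70) x half-width ratio]. For k = 1:

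| assumed CV | planned | r = 0.2 | r = 0.3 | r = 0.5 | r = 0.7 |
|---|---|---|---|---|---|
| 25% | 1.071 | 1.070 | 1.068 | 1.062 | 1.051 |
| 35% | 1.100 | 1.098 | 1.095 | 1.086 | 1.071 |
| 50% | 1.141 | 1.139 | 1.135 | 1.122 | 1.099 |

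The gain is negligible at low r and becomes visible from about r = 0.5.

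**5. Single trials when baseline predicts nothing.** The r = 0 row is an average. In 4,000 simulated trials (140 subjects, 4 sites), one added term widened the interval by more than 1% in about 13% of trials, with a 95th percentile of 1.6% and a 99th of roughly 3%. With the indicator and an assumed 30% of baselines below the limit, the figures were about 37%, 2.6% and roughly 4%.

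**6. Below-limit or missing baselines.** At r = 0.5, the simulated half-width ratio was 0.870 with complete baselines, 0.885 with 30% below the limit, 0.910 with 60% below the limit, and 0.876 with 5% missing. These rates are assumed. The gain shrinks but does not vanish.

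**7. Validity of the planned model.** In 20,000 simulated trials at each of r = 0.3, 0.5 and 0.7 (70 per arm, log SD 0.340, 2 sites), bias in the log ratio was below 0.001 with and without baseline. Coverage of the 90% interval was 0.897 to 0.902 without baseline and 0.897 to 0.901 with it. Mean half-width was 0.095 without baseline, and 0.091, 0.083 and 0.068 with it.

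**8. Exclusions after randomisation.** The PD population (SAP 8) is restricted to dosing-compliant subjects with evaluable data. As an extreme case, suppose one arm alone lost its lowest-baseline 12.5%. The log-ratio shift is r x 0.340 x phi(z)/(1 - 0.125), with z the 12.5% normal quantile: 0.024 at r = 0.3 and 0.056 at r = 0.7, or about 2% and 6% on the ratio.

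**The case against.** The strongest reply is that this is a preference. The planned model contains the design factors, was specified in advance, and is the same in both documents. Everything gained depends on r, and the documents say nothing about it. What they do say is that "Concentrations of CGRP increased in an LY2951742 dose- and concentration-dependent manner, suggesting binding of LY2951742 to CGRP", which points to drug exposure as the driver and leaves the share due to baseline unknown. No PD conclusion hangs on the width, and both documents already allow further analyses (Protocol 10.3; SAP 3).

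Much of this stands. The gain may be nil, and no planned decision would change. What does not stand is that nothing need be done: using a baseline value already collected is a specific change with a small cost, and permission for supplementary analyses does not put the covariate in the planned model.

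A reader might infer more than the documents support:
- **That the device ratio is biased.** Allocation is randomised 1:1, and step 7 shows no bias. Bias would need exclusions that differ by device and relate to baseline, and the documents give no sign of these.
- **That a chance baseline imbalance is a separate harm.** It is part of the same variance that the unadjusted interval already covers.
- **That a PD equivalence test loses power.** No PD range or power is stated.
- **That the SAP departs from the protocol.** It does not.

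**Conclusion.** The point holds as an optional improvement in precision. The planned ANOVA is valid, subject to the condition on PD exclusions. The expected loss is a wider secondary 90% interval: nothing useful below r of about 0.1, around 4% of the log-scale half-width at r = 0.3, 13% at 0.5 and 28% at 0.7. Against that, if r is near zero, the adjusted interval is wider by 0.4% (one term) to 0.8% (two terms) on average, and by roughly 2 to 4% in an unlucky trial.

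These figures rest on 140 PD-evaluable subjects, 4 sites and assumed values of r; the ratio-scale limits also rest on assumed CVs. Primary PK, its acceptance range and its power are untouched. The sponsor could make this change; the plan does not fail without it.

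**What to change.** Before first dosing (SAP 3 requires sign-off by then), add the log of predose CGRP as a continuous covariate to the model for both CGRP parameters in SAP 9.4.2, and in Protocol 10.3.3.2 if the protocol is amended. If it is not, list the change in SAP section 11, which now reports none. Keep the planned ANOVA as a sensitivity analysis.

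State one rule for the covariate only. A workable version sets a below-limit predose value to half the limit, with an indicator if any occur, and a missing value to the mean log baseline pooled over both arms. It should stand apart from SAP 9.3.1.2: read onto an endogenous analyte, those rules would set a below-limit predose value to missing.

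The cost is some wording, one or two model terms out of about 127 to 135 residual degrees of freedom, and one extra analysis. No sample or visit is added. The CGRP parameters remain observed values; whether to subtract baseline from them is a different question that this change does not address.

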### **9.5 Safety and Tolerability Assessments**

#### **9.5.1 Adverse events**

Where changes in severity are recorded in the Case Report Form (CRF), each separate severity of the adverse event (AE) will be reported in the listings, only the most severe will be used in the summary tables. A pre-existing condition is defined as an AE that starts before the subject has provided written informed consent and is ongoing at consent. A non-treatment emergent AE is defined as an AE which starts after informed consent but prior to dosing. A treatment-emergent AE is defined as an AE which occurs postdose or which is present prior to dosing and becomes more severe postdose.

All AEs will be listed. Treatment-emergent AEs will be summarized by treatment, severity and relationship to the study drug. The frequency (the number of AEs, the number of subjects experiencing an AE and the percentage of subjects experiencing an AE) of treatment-emergent AEs will be summarized by treatment, Medical Dictionary for Regulatory Activities (MedDRA) version 19.1 system organ class and preferred term. The summary and frequency AE tables will be presented for all causalities and those considered related to the study drug. Any serious AEs will be tabulated.

#### **9.5.2 Injection Site Reactions**

The number and percentage of subjects experiencing any ISR after dosing will be summarized. Furthermore, the number and percentage of subjects will be presented for each grade category for erythema, induration, pain, and pruritus. A table with number and percentage of subjects by maximum grade will also be presented. Moreover, descriptive statistics will be presented for parameters like erythema, induration etc. as these will also be recorded as the actual maximum linear diameter (to the nearest millimeter) as a continuous variable. These data will also be listed.

#### **9.5.3 Concomitant medication**

Concomitant medication will be coded using the WHO drug dictionary (Version September 2015). Concomitant medication will be listed.

#### **9.5.4 Clinical laboratory parameters**

All clinical chemistry and hematology data will be summarized by parameter and treatment, and listed. Urinalysis data will be listed. Additionally clinical chemistry, hematology and urinalysis data outside the reference ranges will be listed.

Values for any clinical chemistry, hematology and urinalysis values outside the reference ranges will be flagged on the individual subject data listings.

